5.2.3 Protocol Deviations

Protocol deviations, as specified by the monitor, will be categorized into major and minor deviations prior to unblinding and will be listed. Major protocol deviations will be presented as a listing by cohort.

No exploratory analyses is planned on subjects without important protocol violations since this is a safety study.

5.2.4 Demographic and Other Baseline Characteristics

Demographic and other baseline characteristics for the Safety Analysis Set will be summarized for each sequence and overall using descriptive statistics for each cohort separately. Continuous demographic and baseline variables include age height, and weight; body mass index (BMI); categorical variables include sex, age group (<65, and >= 65 years), BMI group, race, and ethnicity.

MEDICAL HISTORY

The number (percentage) of subjects in the Safety Analysis Set reporting a history of any medical condition, as recorded on the CRF, will be presented as a listing by cohort. A subject data listing of medical and surgical history will be provided.

5.2.5 Prior and Concomitant Therapy

All investigator terms for medications recorded in the CRF will be coded to an 11-digit code using the World Health Organization Drug Dictionary (WHO DD) (Mar 2017 or latest version). The number (percentage) of subjects who took prior and concomitant medications will be presented as a listing by cohort. Prior medications will be defined as medications that stopped before the first dose of study drug. All medications will be presented in subject data listings.

Concomitant medications are defined as medications that (1) started before the first dose of study drug and are continuing at the time of the first dose of study drug, or (2) started on or after the date of the first dose of study drug to the last dose day plus 14 days. All medications will be presented in subject data listings.

5.2.6 Treatment Compliance

Compliance for the OSA Cohort each study drug will be calculated on the basis of the number of tablets dispensed, lost and returned, separately for each row of tablets and overall, for all randomized subjects.

$$\text{Compliance} = \frac{\text{Total number of tablets dispensed} - \text{total number of tablets returned or lost}}{100} \times \text{Number of tablets expected to be taken by the subject for the treatment period}$$

Summaries will provide descriptive summary statistics and number (percentage) of subjects using the categories <80%, >= 80% to <= 100%, >100% to <= 120%, and > 120% for each treatment group.

Subjects in the HV Cohort will receive 1 dose of study medication per period while in clinic. Treatment compliance will not be calculated for this cohort.

5.3 Data Analysis General Considerations

5.3.1 Pooling of Centers

This study is a multicenter study across the United States, with approximately 10 sites. Due to the small sample size and the fact that this is a safety study, analysis will be based on pooling of data from different sites and there will be no by site analysis.

Pooling will be performed for each cohort independently based on each cohort's sites.

5.3.2 Adjustments for Covariates

Since this is a crossover study, there will be no adjustment for covariates like age, gender, race, ...etc. The model will include fixed effects for sequence, period, and treatment, and a random effect for subject within sequence.

5.3.3 Multiple Comparisons/Multiplicity

No multiplicity adjustments will be made. This is a phase I safety study.

5.3.4 Examination of Subgroups

Subgroup analysis of PD endpoints will be performed by age group (adults versus elderly) for the OSA Cohort.

5.3.5 Handling of Missing Data, Dropouts, and Outliers

In general, missing values due to subject discontinuation, missed or unusable assessments will not be imputed.

Incomplete/Missing data will not be imputed, unless otherwise specified; i.e., all missing values will remain as missing in all statistical analyses and listings, unless otherwise specified.

Outliers: No formal statistical analyses will be performed to detect and/or remedy the presence of statistical outliers.

5.3.6 Other Considerations

Individual subject data in the database will be presented in data listings.

5.3.7 Visit Window

All data will be presented using nominal visits as reported in the data. No additional derivation will be performed for analysis visit window.

5.4 Efficacy Analyses

No efficacy data will be recorded for this study.

5.4.1 Primary Pharmacodynamic Analyses

Analysis for the Primary Endpoint

HV Cohort: Mean SpO₂ during TST will be analyzed using a mixed effect model. The model will include fixed effects for sequence, period, and treatment, and a random effect for subject within sequence. The following will be presented: least squares (LS) means, difference in LS mean of lemborexant 10 mg and lemborexant 25 mg compared to placebo, a two-sided 90% CI (equivalent to a one-sided lower 95% CI) for the true mean difference (lemborexant – placebo) in SpO₂ and *p*-value. If the lower bound of the one-sided 95% CI of the treatment difference of SpO₂ is less than -5, this will provide evidence that the given dose of lemborexant does not result in a clinically significant decrease in SpO₂ compared to placebo.

OSA Cohort: AHI will be analyzed using a mixed effect model. The model will include fixed effects for sequence, period, and treatment, and a random effect for subject within sequence. The following will be presented: LS means, difference in LS mean of lemborexant 10 mg compared to placebo, a two-sided 90% CI (equivalent to a one-sided upper 95% CI) for the true mean difference (lemborexant – placebo) in AHI and *p*-value. If the upper bound of the one-sided 95% CI of the treatment difference of AHI is less than 5, this will provide evidence that the given dose of lemborexant does not result in a clinically significant increase in AHI with mild OSA compared with placebo.

A sensitivity analysis may also be performed on the primary endpoint where outliers are excluded. Other sensitivity analyses may be explored.

Plots of AHI and SpO₂ treatment difference data (both individual and LS Mean) will be used to explore the results.

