9.7.2 Determination of Sample Size

HV Cohort

A mean difference of 5 percentage points between treatments in SpO₂ is considered to be clinically meaningful in a study of the respiratory safety of suvorexant in healthy adult

volunteers (Uemura, et al., 2015). From that source, the within-subject variance is assumed to be 0.315%. With a total of 12 subjects (4 elderly and 8 adults) completing the study and assuming that the true difference between treatments is -1.0, there is 99% power that the lower bound of the 90% confidence interval for the difference in SpO₂ (lemborexant - placebo) would be greater than -5. Although the estimate of within-subject variability is based on a study of adult healthy volunteers, the addition of elderly subjects is expected to have a minimal effect on the combined variability and thus a minimal effect on the power.

OSA Cohort

A mean difference between treatments in AHI > 5 is considered clinically meaningful in studies of the respiratory safety of sleep agents in OSA (Kryger, et al., 2007, Sun, et al., 2016). The within-subject variance is assumed to be 25.34 for AHI for adult subjects (Sun, et al, 2016) and 30.41 for AHI for elderly subjects (where the elderly within-subject variance is estimated from adult data + 20% (Mitterling, et al, 2015; Lee, et al., 2016). Assuming the true difference in AHI (lemborexant – placebo) on Day 8 is as high as 1.5, a total of 30 subjects completing the study (20 adult, 10 elderly), provides 82% power that the upper bound of the 90% CI for the treatment difference in AHI (lemborexant – placebo) on Day 8 would be < 5.

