3.1 Study Objectives

3.1.1 Primary Objectives

Primary Objective (Healthy Volunteer [HV] Cohort)

To determine whether lemborexant decreases the peripheral oxygen saturation (SpO₂) during total sleep time (TST) in healthy adult and elderly subjects after a single dose of treatment compared with placebo

Primary Objective (Obstructive Sleep Apnea [OSA] Cohort)

To determine whether lemborexant increases the AHI after multiple doses of treatment in adult and elderly subjects with mild OSA compared with placebo

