4 DETERMINATION OF SAMPLE SIZE

Sample Size Rationale

HV Cohort:

A mean difference of 5 percentage points between treatments in SpO₂ is considered to be clinically meaningful in a study of the respiratory safety of suvorexant in healthy adult volunteers (Uemura, et al., 2015). From that source, the within-subject variance is assumed to be 0.315%. With a total of 12 subjects (4 elderly and 8 adults) completing the study and assuming that the true difference between treatments is -1.0, there is 99% power that the lower bound of the 90% confidence interval for the difference in SpO₂ (lomborexant - placebo) would be greater than -5. Although the estimate of within-subject variability is based on a study of adult healthy volunteers, the addition of elderly subjects is expected to have a minimal effect on the combined variability and thus a minimal effect on the power.

OSA Cohort: A mean difference between treatments in AHI > 5 is considered clinically meaningful in studies of the respiratory safety of sleep agents in OSA (Kryger, et al., 2007, Sun, et al., 2016). The within-subject variance is assumed to be 25.34 for AHI for adult subjects (Sun, et al, 2016) and 30.41 for AHI for elderly subjects (where the elderly within-subject variance is estimated from adult data + 20%, Mitterling, et al, 2015; Lee, et al, 2016). Assuming the true difference in AHI (lomborexant – placebo) on Day 8 is as high as 1.5, a total of 30 subjects completing the study (20 adult, 10 elderly), provides 82% power that the upper bound of the 90% CI for the treatment difference in AHI (lomborexant – placebo) on Day 8 would be < 5.

Sample Size Estimates for OSA Cohort

Description	Combined within-subject variance of AHI	Adult N	Elderly N	Total N	Total Power (%)
80% overall power with 20 adult subjects	26.96	20	10	30	82
85% overall power with 20 adult subjects	27.38	20	14	34	86
80% overall power with 20 elderly subjects	28.54	12	20	32	82
85% overall power with 20 elderly subjects	28.16	16	20	36	86
Equal number of subjects	27.875	20	20	40	90

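### The healthy-volunteer SpO₂ success criterion is written backwards: it is met when the lower confidence bound falls below -5, not when it stays above

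*SAP*

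**What the plan says.** The HV primary objective (SAP section 3.1.1) begins "To determine whether lemborexant decreases the peripheral oxygen saturation", so the harm of interest is a fall. SAP section 5.4.1 estimates a confidence interval "for the true mean difference (lemborexant – placebo) in SpO₂", described as "a two-sided 90% CI (equivalent to a one-sided lower 95% CI"). Section 4 of the SAP sets the margin: "A mean difference of 5 percentage points between treatments in SpO₂ is considered to be clinically meaningful".

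The decision rule in section 5.4.1 then says that if the lower bound "is less than -5, this will provide evidence that the given dose of lemborexant does not result in a clinically significant decrease in" SpO₂, the dose has met the criterion. It is applied separately to 10 mg and 25 mg. The same sentence stands in protocol section 9.7.1.7.2 and in the synopsis under the analysis of the primary endpoint.

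The sample-size text points the other way. Protocol section 9.7.2, the synopsis sample-size rationale and SAP section 4 each claim 99% power that the lower bound "would be greater than -5".

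**The concern.** When harm is a negative difference, a lower bound below -5 means that a clinically meaningful fall has not been excluded. The plan treats that outcome as evidence of no such fall. Taken literally, a dose that clearly lowers SpO₂ by more than 5 points meets the criterion, and a dose with no effect does not.

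The study is also powered for one event and judged on its complement. Nothing in the analysis sections says that the sample-size wording takes precedence, and SAP section 7 records no changes to the planned analyses. The report would therefore have to either follow the printed rule and draw the wrong conclusion, or depart from a pre-specified primary criterion once the results are known.

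**Working it through.** **Inputs** (SAP section 4 and section 5.4.1)

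- Margin: -5 percentage points, for lemborexant minus placebo.
- Variance: "the within-subject variance is assumed to be 0.315". The plan prints a percent sign after the number; I read it as squared percentage points.
- Planning value: "assuming that the true difference between treatments is -1.0".
- 12 completers in a three-period, three-sequence crossover, taken as 4 per sequence.
- One-sided 5% level, from the two-sided 90% interval.

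**Precision**

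- SE of a treatment difference = √(2 × 0.315 / 12) = 0.229.
- Residual degrees of freedom = 36 observations − 12 subjects − 2 periods − 2 treatments = 20, so t(0.95, 20) = 1.725.
- Half-width from estimate to lower bound = 1.725 × 0.229 = 0.395.

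**Reproducing the stated power**

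For a true difference δ, P(lower bound > -5) is the probability that a noncentral t on 20 df, with noncentrality (δ + 5)/SE, exceeds 1.725. At δ = -1.0 the noncentrality is 4 / 0.229 = 17.5, and the power is above 99.99%. The plan's 99% is thus a conservative statement of the probability of a bound *above* -5. For power of exactly 99% the variance would have to be about 5.7. Under the printed direction the same scenario gives about 0%, because the expected lower bound is about -1.0 − 0.395 = -1.40, far above -5.

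**What the printed rule does**

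It is met only when the observed difference is below about -5 + 0.395 = -4.6. The two directions are complementary:

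| True difference | Met as printed (bound < -5) | Met if reversed (bound > -5) |
|---|---|---|
| 0 | about 0% | about 100% |
| -1 (planning value) | about 0% | about 100% |
| -4 | about 0.5% | about 99.5% |
| -5 (at the margin) | 95.0% | 5.0% |
| -5.5 | 99.99% | 0.008% |
| -6 | more than 99.99% | less than 0.01% |

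Simulation of the 3 × 3 design (50,000 runs per row, subject, period and treatment as fixed effects) agrees with the noncentral t values. In the reversed column the probability at the margin is 5%, the nominal one-sided error rate. As printed it is 95%.

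**Sensitivity**

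- With 10 or 11 df instead of 20, the half-width is 0.41 to 0.42 and the pattern is the same.
- Reading 0.315 as a standard deviation, or as the variance of the difference, leaves power for a bound above -5 above 99.99%.
- With ten times the variance (3.15), SE = 0.725. The printed rule is then met about 0.01% of the time at -1 and 95% at -5.

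**Comparison with the OSA rule**

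SAP section 5.4.1 asks for the upper bound of the AHI difference to be less than 5. Harm there is positive, so that direction is right.

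**The case against.** The strongest reply is that nobody would be misled. The sample-size text gives the right direction in three places, the stated power makes sense only that way, the OSA rule is correctly directed, and the estimate with its 90% interval will be reported whatever the rule says. On this view it is a drafting slip and not a choice of method. That description is fair, and it is why the fix is easy. It does not make the fix optional: the sentence is the only stated criterion for the HV primary endpoint, and it is wrong in every place where it appears as the rule.

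Two limits on the size of the point do stand. First, the rule only says when there is evidence of no clinically significant decrease. It does not formally declare a dose safe, nor say what follows when the condition is not met. Second, true falls of 5 points or more are far from the planning value of -1.0. The likelier practical consequence is that a benign result fails to meet the printed criterion, so that the planned conclusion is unavailable under the plan's own words.

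This is not a text-extraction fault. The inequality is spelled out in words, identically in all three places.

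**Conclusion.** The concern holds and must be fixed. As printed, the criterion is met about 0% of the time in the scenario the study was sized for, and 95% of the time when the true fall equals the margin.

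The exact percentages assume a within-subject variance of 0.315 squared percentage points, 12 completers balanced over the sequences, and 20 residual degrees of freedom. The inversion itself depends on none of these: it follows from the sign of the contrast and the margin, and any variance gives 95% at a true difference of -5. The consequence for the trial's conclusion depends on the rule being applied literally.

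**What to change.** In SAP section 5.4.1, protocol section 9.7.1.7.2 and the synopsis analysis of the primary endpoint, restate the HV criterion so that the lower bound of the one-sided 95% interval for the SpO₂ difference must be greater than -5. Leave the OSA criterion and the sample-size text as they are.

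The edit is one word in three places, with no change to data, model, sample size or power. It does need paperwork. Protocol section 11.1 requires a written amendment or administrative change approved by the sponsor, and SAP section 3 requires modifications and their rationale to be documented and approved before unblinding. Making the correction then means that the right rule is the pre-specified one when the results are read.

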5.4.2 Secondary Pharmacodynamic Analyses

Analysis for the Secondary Endpoints

The continuous secondary endpoints for both cohorts will be analyzed using the same model as the primary endpoint. Treatment comparison will be performed using contrasts.

The proportion of subjects with SpO₂ <90% will be summarized using descriptive statistics. All analyses will be performed separately for each cohort.

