Mean oxygen saturation%	95.2 (93.0–97.5)	95.5 (92.5–98.0)	95.0 (90.0–98.0)	93.8 (91.0–96.3)	93.5 (89.3–96.6)	0.001
Minimal oxygen saturation%	90.0 (84.0–95.0)	91.0 (86.0–95.0)	89.5 (81.0–94.0)	88.0 (78.0–93.0)	87.0 (80.0–98.0)	0.014

Data are shown as median and range.

AHI = apnea-hypopnea index.

Data from Mitterling, et al., 2015.

Given the changes in respiratory function with age even in healthy individuals, the increasing prevalence of both insomnia and OSA with age, and the coexistence of the 2 conditions in many patients, it is important to examine the safety in OSA of agents that are under development for sleep disorders.

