8.2 Secondary Objectives

8.2.1 HV

The secondary objectives of the study for the HV cohort are:

1. Determine whether lemborexant increases the apnea-hypopnea index (AHI) after a single dose of treatment compared with placebo
2. Determine whether lemborexant decreases SpO₂ during TST below defined thresholds after a single dose of treatment compared with placebo (revised per Amendment 01)
3. Evaluate safety and tolerability of lemborexant

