9.3.5 Additional Exclusion Criteria (HV Cohort)

25. Any valid event of SpO₂ <90% during the Screening PSG
26. Current evidence of a clinically significant, active respiratory disorder. This includes bronchiectasis, emphysema, asthma, chronic obstructive pulmonary disease, or any other pulmonary disorder identified by review of medical history, physical examination, and which in the opinion of the investigator, could compromise the subject's safety or interfere with study assessments.
27. Presence of significant illness (including insomnia) that requires treatment or may influence the study assessments (e.g. psychiatric disorders, disorders of the gastrointestinal tract, liver, kidney, respiratory system, endocrine system, hematological system, neurological system, cardiovascular system, or a congenital abnormality), malignancy within the past 5 years (other than adequately treated basal cell carcinoma or in situ carcinoma of the cervix), or chronic pain that in the opinion of the investigator could interfere with the study assessments. Subjects for whom a sedating drug would be contraindicated for safety reasons because of the subject's occupation or activities are also excluded.

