5 STATISTICAL METHODS

All analysis will be reported separately for each cohort. All descriptive statistics for continuous variables will be reported using mean, standard deviation (SD), median, minimum and maximum. Categorical variables will be summarized as number (percentage) of subjects.

All statistical tests will be based on the 5% level of significance (2-sided), unless otherwise stated. If statistical comparisons are not defined, all pairwise comparisons will be tested.

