5.1.2 Secondary Endpoints

Secondary Endpoints (HV Cohort)

1. The AHI on Day 1 of treatment
2. The percentage of TST during which SpO₂ is <90%, <85% and <80% on Day 1 of treatment
3. The proportion of subjects with at least one incident of SpO₂ <90% for at least 30 seconds during TST on Day 1 of treatment

Secondary Endpoints (OSA Cohorts)

1. The AHI on Day 1 of treatment
2. The mean SpO₂ during TST on Day 1 and Day 8 of treatment
3. The percentage of TST during which the SpO₂ is <90%, <85% and <80% on Day 1 and Day 8 of treatment
4. The proportion of subjects with at least one incident of SpO₂ <90% for at least 30 seconds during TST on Day 1 and Day 8 of treatment.

Exploratory Endpoints (HV and OSA Cohorts)

1. The mean SpO₂ during REM sleep, NREM and wake
2. The AHI during REM and NREM sleep
3. The AHI separately for adult and elderly subjects at all days assessed
4. The mean SpO₂ during TST separately for adult and elderly subjects at all days assessed

Pharmacokinetic Endpoint (HV and OSA Cohorts)

Lemborexant and metabolites M4, M9 and M10 plasma concentrations

Pharmacokinetic/Pharmacodynamic (Exposure-Response) Endpoint (HV and OSA Cohorts)

Correlations between plasma concentrations of lemborexant and select pharmacodynamic variables including AHI, mean SpO₂ during TST, and proportion of TST in which SpO₂ is <90%, <85% and <80% at all days assessed.

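### Does the SAP need a rule for the time-below-threshold SpO₂ endpoints when nearly all healthy-volunteer values are zero?

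*SAP*

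**What the plan says.** SAP 5.1.2 lists as an HV secondary endpoint: "The percentage of TST during which SpO₂ is <90%, <85% and <80% on Day 1 of treatment". The OSA cohort has the same measure on Days 1 and 8. SAP 5.4.2 sets the method: "The continuous secondary endpoints for both cohorts will be analyzed using the same model as the primary endpoint". That model (SAP 5.4.1) is a Gaussian mixed model with sequence, period and treatment as fixed effects and subject within sequence as random. Nothing is said about transformation, an exact method or a minimum number of non-zero values. On outliers, SAP 5.3.5 says: "No formal statistical analyses will be performed to detect and/or remedy the presence of statistical outliers". SAP 8 deals only with missing data.

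The endpoint serves a secondary objective in Protocol 8.2.1: "Determine whether lemborexant decreases SpO₂ during TST below defined thresholds after a single dose of treatment compared with placebo". HV entry is restricted by Protocol 9.3.5, which excludes on "Any valid event of SpO₂ <90% during the Screening PSG", and Protocol 9.3.2 requires AHI below 5.

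Three reporting provisions also apply:

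- SAP 5: "All descriptive statistics for continuous variables will be reported using mean, standard deviation (SD), median, minimum and maximum".
- SAP 5.3.6: "Individual subject data in the database will be presented in data listings".
- SAP 5.4.2: the subject-level endpoint (at least one spell below 90% lasting 30 seconds or more) is summarised descriptively.

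**The concern.** A percentage of sleep time below 85% or 80% in healthy people screened for desaturation may be zero on nearly every night. A Gaussian model suits such data poorly, and two failures are possible.

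- If all 36 subject-nights are zero, the residual variance is zero. The interval then collapses to [0, 0] or the fit fails.
- If the few non-zero values all fall on drug, the estimate and its standard error are small together, and the upper bound can lie below the true difference more often than the nominal 5%.

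In a respiratory safety study, a [0, 0] interval could be misread as proof of no risk, when zero affected subjects of 12 still leaves a sizeable rate possible. A fallback chosen after unblinding would also be open to question.

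**Working it through.** **The plan's own figure.** SAP 4 gives no figure for these percentages. Its HV figure is 99% power for mean SpO₂, with n = 12, within-subject variance 0.315, true difference -1 and margin -5. SE = √(2 × 0.315 / 12) = 0.229, and (-1 + 5) / 0.229 = 17.5 against a critical t of 1.725 on 20 df. Power exceeds 99.9%, so the stated figure is met. It says nothing about time below threshold.

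**Is sparsity plausible?** Protocol Table 1 reports "Minimal oxygen saturation" by decade in healthy sleepers. Medians run from 87% to 91%, and only the 51–60 group has a range reaching below 80% (78.0–93.0). Those sleepers were not selected as the HV are: their AHI ranges reach 25.0. Mostly-zero data are therefore likely below 80%, plausible below 85% and uncertain below 90%. This is inference from one screening night; the documents give no data on these percentages.

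**All-zero probability (assumed rates, independent nights).** If no placebo night and a share p of nights on each dose is non-zero, P(all zero) = (1 - p)^24:

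- p = 5%: 0.95^24 = 29%
- p = 10%: 0.90^24 = 8%
- p = 20%: 0.80^24 = 0.5%
- 5% on one dose only: 0.95^12 = 54%

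**What the model returns.** With all values zero and subject fixed, estimate, SE and 90% interval are all 0; a REML mixed-model fit did not converge and gave undefined SEs. With a single non-zero night (1% of TST on 25 mg), 10 mg versus placebo gives 0 ± 1.725 × 0.068 = ±0.117, although both of those arms are entirely zero. The width comes from the other dose.

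**Coverage of a nominal one-sided 95% upper bound, among trials that yield an interval.** Simulation of 12 subjects (4 per sequence) with subject, period and treatment effects on 20 df. Non-zero values are lognormal with an assumed mean of 2% of TST.

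| Non-zero share (placebo/10 mg/25 mg) | log-SD 0.5 | log-SD 1.0 | log-SD 1.5 |
|---|---|---|---|
| 0/5/5% | 98% | 84% | 66% |
| 0/10/10% | 92% | 79–80% | 64% |
| 0/20/20% | 92% | 83% | 69% |
| 0/0/5% (25 mg) | 99.6% | 86% | 65% |

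Two further settings at log-SD 1:

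- Equal shares of 10% on all treatments: about 97%.
- No placebo events but 80% of nights non-zero on both doses: still only 91%, although zeros on drug are then uncommon.

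A random subject effect with variance held at or above zero gives nearly the same figures.

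**Size of a miss.** In the four drug-only settings at log-SD 1, the median shortfall is 0.037, 0.081, 0.128 and 0.034 points of TST. TST cannot exceed the 8-hour recording (28,800 s), so the extremes are at most 0.0003 × 28,800 ≈ 9 s and 0.0013 × 28,800 ≈ 37 s. The shortfall scales with the assumed 2% mean.

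**Would a formal rule help?** Take a blinded cut-off that sets the model aside when fewer than 12 of 36 nights are non-zero.

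- With equal shares of 10%, coverage is 97%, yet nearly every trial falls under the cut-off.
- With equal shares of 20%, coverage is 96%, and 96% of trials fall under it.
- With drug-only events averaging 12 to 19 non-zero nights, so at or above the cut-off, coverage is still only 89–91%.

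The rule does not separate sound intervals from poor ones. Exact one-sided 95% bounds per treatment (0/12: 1 - 0.05^(1/12) = 22%; 0/30: 9.5%) follow from the counts alone. An exact paired test needs five subjects affected on drug only and none on placebo only for one-sided p = 0.5^5 = 0.031.

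**The case for a change.** The best case for a change is that the gap is real and cheap to close. No clause in the SAP or protocol covers sparse data, the optional sensitivity analyses name no method, and the logistic example in SAP 13.3 is tied to no analysis in the text. Medians, ranges and listings show what was observed but not what remains possible, and 0 of 12 is compatible with a true rate of up to 22%. Settling the fallback before unblinding would prevent an after-the-fact choice.

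The textual point stands, and so does the all-zero failure. The rest carries less weight. Any reader can see that 0 of 12 is weak evidence, and minimum = maximum = 0 shows at once why no interval exists. Per-treatment bounds are not a comparison with placebo, which is what the objective asks for, and counting any time below threshold discards duration. The coverage figures also assume the 90% two-sided level of the primary analysis. SAP 5.4.2 carries over the model without stating that level, and SAP 5 defaults to 5% two-sided. At that level the bounds cover 87%, 83% and 87% against a nominal 97.5% in the first three drug-only settings (log-SD 1). The pattern is the same, but the size depends on the reading. Table shells and programming specifications are separate documents (SAP 9 and 11) and may already say what is printed when a model cannot be estimated.

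**Conclusion.** No change is needed. SAP 5.4.2 does omit what to report when a threshold has all or nearly all zero values, most plausibly in HV below 80% and 85%. An analyst meeting such a table would report it descriptively and leave the model interval uninterpreted, and the summaries and listings needed for that are already required. No margin, sample size, primary result or pass/fail conclusion depends on it.

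The too-narrow interval is conditional. It needs events concentrated on drug and a wide spread of values: coverage is 92–99.6% at log-SD 0.5, 64–69% at log-SD 1.5, and about 97% when treatments share a 10% rate. At log-SD 1 the typical miss is 0.03 to 0.13 points of TST. A formal cut-off would mostly set aside sound intervals. All rates, sizes and spreads are assumptions, nights are taken as independent, and the documents give nothing to calibrate them. If non-zero values were much larger than 2% of TST the shortfall would grow in proportion, but such subjects would stand out in the maximum and the listings.
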